Participants will be recruited from the greater Los Angeles community using advertisements. All interested participants will first complete a structured telephone interview in order to assess eligibility; prospective participants with co-morbid medical conditions or characteristics known to affect inflammation or put them at undue risk will be ineligible to participate. Notably, participants with current Major Depressive Disorder will be excluded. However, we will control for depressive symptoms in analyses examining effects on loneliness to test whether the effect of NSAIDs on loneliness hold over and above effects on depression.

At baseline, participants will complete their first session online with an experimenter. Here, they will provide blood spots, complete self-report measures as well as several psychological tasks. Psychological tasks will include a task in which participants view negative social images and make ratings of their affective responses. Participants will also include a social/monetary reward task (revised Monetary Incentive Delay Task; Knutson et al., 1999) in which they will press a button once a target flashes on the screen in order to win money or see a close other or smiling stranger. Reaction times will be assessed, with faster reaction times indicating greater reward anticipation. We are

particularly interested in the difference in reaction times to close others vs. control targets.

They will be mailed their pill packs for the intervention. Following the baseline assessment, participants will take one 200 mg pill immediately after waking up each day, and another 200 mg pill an hour before going to sleep, daily for 2 weeks. By random assignment, half of the participants will take naproxen and half will take the same dose of placebo. The random allocation sequence will be generated by a statistical consultant who was not involved in running participants and will be kept by the UCLA Pharmacy to ensure proper drug preparation for each participant. Randomization will be done using a computerized uniform random number generator; males and females will be randomized separately in permuted blocks of 4.

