Naproxen was chosen as it is available as a generic (and thus low-cost) drug, has a less frequent dosing schedule (i.e., twice daily) than some other NSAIDs (e.g., ibuprofen, taken every 4-6 hours), and has been associated with lower risk for adverse cardiovascular side effects compared to other NSAIDs. Furthermore, naproxen can reduce depressive symptoms in both animals and humans, providing evidence that it can affect psychological states. Additionally, the effect of NSAIDs on circulating levels of inflammation are inconsistent, but there is some meta-analytic evidence to suggest that naproxen specifically may lead to significant decreases in C-reactive protein, suggesting naproxen may be one of the best NSAIDs for reducing circulating levels of inflammation. The dosing of 400 mg/daily was chosen based on maximum over-the-counter recommendations.

Over the 2-week period, subjects will complete daily and weekly (online) measures of loneliness, other social psychological outcomes, and any side effects. Additionally, participants will receive text message reminders to take their pills, and report on symptoms, adherence, and any side effects (monitored by study staff). Participants will be asked to report on a full range of symptoms (mild, moderate, severe) in both a checklist and an open-ended fashion. Adverse events will be reported to the study physician, who will not be blinded to condition. If, at any point in the study, participants report mild side effects (e.g., diarrhea, heartburn for 2 consecutive days or more), their dose will be reduced by half to 200 mg each day. If participants report moderate to severe side effects (e.g., stomach pain, shortness of breath or trouble breathing), they will be removed from the study. At the end of the 2-week intervention, participants will get online again with an experimenter to provide another blood sample (to be mailed back) as well as to complete self-report measures and behavioral tasks, similar to the baseline assessment. In addition, participants will be contacted again 2 weeks later to assess measures of loneliness.

IRB amendment (5/2021):

Major changes to study protocol for COVID and financial reasons

Minor Amendment - Types of change(s) proposed.

Check all that apply:

- Clarification or technical change
- **Minor increase/decrease in number of Study participants**
- Narrowing of the inclusion criteria

- Broadening of the exclusion criteria

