- **Changes in the dosage or form (e.g., tablet to liquid) but not the route of administration of an approved drug**
- **Increase or decrease in the number of safety monitoring visits provided that there is no impact on subject safety.**
- Addition or deletion of study sites
- **Change in payments to study participants**
- **Minor changes to recruitment materials**
- **Minor changes to screening procedures**
- **Change in funding (for example, addition of new funding or completion of grant) – Please describe below AND update the funding status in section 6.2 in the main application**
- **Other**

Major Amendment - Types of change(s) proposed.

Check all that apply:

- **Change in study design of a protocol approved by the full board of the IRB**
- Change in status of study participants (e.g., study participant becomes prisoner, ward, or pregnant in a protocol not approved for these populations (Note: This primarily applies to medical or treatment studies.)
- Addition of a procedure not approvable using expedited review procedures (e.g., ionizing radiation)
- Changes that increase risk or discomfort to study participants
- **Substantive changes to a consent form or other study documents distributed to subjects.**
- **Other**

Numerous reasons have converged and required us to change this study protocol drastically. First, because of the COVID-19 pandemic, we want to minimize all in-person contact as much as possible for participants and staff. Second, the budget/finances available to run this study have been drastically reduced because the pandemic as well. As such we are proposing the following changes to the study:

- Instead of n=100, we will have a final sample of n=50 (necessary for cost-saving)
- As the inflammatory markers were only an exploratory aim of the study, we will be eliminating all inflammatory markers / blood draws from the study for cost-saving reasons, as well as to be able to allow participants to complete the study entirely from their own homes for COVID safety reasons. All references to blood draws, inflammatory markers, gene expression analyses, medical records, medical tests, UCLA health phlebotomy, etc. have been removed from all materials/throughout the IRB.

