- All participant payments and time required has also been updated to reflect the shortened study design

IRB amendment (7/2021):

Study amended to include blood spot collection for inflammatory assessment. Blood spot collection devices will be mailed to participants and sent back to us for analysis.

Statistical Analysis Plan

Primary:

To examine whether naproxen reduces feelings of loneliness, we will use repeated measures analyses to examine time (pre- vs. post-intervention) by condition (naproxen vs. placebo) interactions on loneliness.

To examine whether naproxen reduces sensitivity to social threat, we will use repeated measures analyses to examine time (pre- vs. post-intervention) by condition (naproxen vs. placebo) interactions on self-reported ratings to negative social images. We anticipate that subjects in the naproxen (vs. control) condition will rate negative images as less negative from pre-to-post intervention.

To examine whether naproxen reduces sensitivity to social reward, we will use repeated measures analyses to examine time (pre- vs. post-intervention) by condition (naproxen vs. placebo) interactions on reaction times to social reward (with faster reaction times indicative of greater reward). Specifically, we expect that subjects in the naproxen (vs. placebo) condition will show less of a difference in reaction times to viewing close others vs. control targets from pre- to post-intervention.

Secondary:

To examine whether naproxen reduces inflammatory gene expression, we will use repeated measures to examine time (pre- vs. post-intervention) by condition (naproxen vs. placebo) interactions on the inflammatory gene composite measure.

To examine whether naproxen reduces feelings of loneliness at follow-up (2 weeks post-intervention), we will use repeated measures analyses to examine time (pre- vs. post- vs. follow-up intervention) by condition (naproxen vs. placebo) interactions on loneliness.

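### The primary social-reward test should name the control-minus-close-other reaction-time difference as its outcome, identify the control trial type, and adjust for baseline

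*Combined protocol and SAP*

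**What the plan says.** Under Statistical Analysis Plan, Primary, the third analysis has the aim "To examine whether naproxen reduces sensitivity to social reward". Its test is a repeated-measures time by condition interaction, with these words for the outcome: "interactions on reaction times to social reward (with faster reaction times indicative of greater reward". Target type is not a factor and no difference score is named. The following sentence gives the expectation that naproxen participants "will show less of a difference in reaction times to viewing close others vs. control targets from pre- to post-intervention".

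The Study Protocol's description of the task says the team is "particularly interested in the difference in reaction times to close others vs. control targets". It describes pressing a button "in order to win money or see a close other or smiling stranger". It does not say which of these serves as the control target.

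The task is done at baseline, and after two weeks participants again "complete self-report measures and behavioral tasks, similar to the baseline assessment". Allocation is equal: "half of the participants will take naproxen and half will take the same dose of placebo". The IRB amendment of 5/2021 sets the size: "we will have a final sample of n=50 (necessary for cost-saving". That gives about 25 per arm. The documents give no reaction-time means, SDs or expected effects.

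**The concern.** The test sentence and the hypothesis sentence describe different estimands. A time by condition effect on raw reaction time to social targets picks up any drug-related change in speed, whether or not it is specific to close others. The hypothesis is about a change specific to close others relative to control. A significant result on raw reaction time therefore need not mean reduced sensitivity to social reward.

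This is one of three primary outcomes, and two choices are left to the analyst: differenced or undifferenced, and which trial type is subtracted. A third matter is efficiency. With one pre and one post measurement, the time by condition interaction is a two-sample comparison of change scores. In a trial of 50 that gives away precision which the baseline measurement could supply.

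**Working it through.** The plan has no figure for this test to reproduce. The inputs from the documents are 25 per arm and two sessions. Everything in milliseconds below is an assumption, as is the two-sided 5% level.

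**1. Model.** Reaction time = person + session effect (SD s, shared by all trial types) + cell noise (SD c). Close-other time is control time minus a person-level advantage. Both s and c range over 10, 20 and 30 ms.

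- Change in close-other time: SD = √(2(s² + c²)).
- Change in the control-minus-close difference: person and session cancel within a session, leaving variance 2c² from noise at each session. The change therefore has variance 4c² and SD 2c.
- Power comes from the noncentral t on 48 df, with noncentrality effect / (SD × √(2/25)).

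**2. Equivalence.** With two target types, time by condition on the difference is the same test as time by condition by target on raw times. In one simulated data set of 50, both gave F = 2.849 on 1 and 48 df.

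**3. The two readings on the same data.** Suppose the drug slowed every response equally, with no change in reward. The shift cancels in the difference, which rejected in 4.8–5.3% of simulated trials. A selective effect means that only close-other responses slow, by 15 ms.

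| s / c (ms) | Raw close-other, general 20 ms | Raw close-other, general 10 ms | Selective 15 ms: raw / difference |
|---|---|---|---|
| 10/10 | 93% | 41% | 74 / 74% |
| 10/20 | 59% | 20% | 38 / 25% |
| 10/30 | 34% | 12% | 21 / 14% |
| 20/10 | 59% | 20% | 38 / 74% |
| 20/20 | 41% | 14% | 25 / 25% |
| 20/30 | 27% | 10% | 17 / 14% |
| 30/10 | 34% | 12% | 21 / 74% |
| 30/20 | 27% | 10% | 17 / 25% |
| 30/30 | 21% | 9% | 14 / 14% |

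For a selective effect the difference is more powerful in three settings, equal in three and less powerful in three.

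If slowing is proportional rather than additive, the difference moves by (20 / mean time) × advantage. With means of 250–400 ms and advantages of 10–40 ms, that runs from 20/400 × 10 = 0.5 ms to 20/250 × 40 = 3.2 ms, and the difference is significant in 5.0–8.6% of trials.

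The choice matters even without general slowing. At s = c = 20 and a selective 15 ms effect, the two tests disagree on significance in about 26% of simulated trials. With no effect at all they disagree in about 8%.

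**4. Baseline adjustment.** Let r be the pre-post correlation of the difference and σ² its variance at one session. The change score has variance 2σ²(1 − r). ANCOVA has residual variance σ²(1 − r²). The ratio is (1 − r²) / (2(1 − r)) = (1 + r)/2. Chance baseline imbalance multiplies this by about 1 + 1/46, so the ratio is below 1 when r < 2/(1 + 1/46) − 1 = 0.957. The change-score SD is held at 2c, the effect is a selective 15 ms, and ANCOVA has 47 df.

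| r | Variance ratio | Power, c = 10 | Power, c = 20 | Power, c = 30 |
|---|---|---|---|---|
| change score | 1 | 74% | 25% | 14% |
| 0 | 0.51 | 95% | 44% | 23% |
| 0.3 | 0.66 | 89% | 36% | 19% |
| 0.6 | 0.82 | 82% | 30% | 16% |
| 0.9 | 0.97 | 75% | 26% | 14% |

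As r approaches 1, ANCOVA power falls to 72.9% against 73.8% at c = 10, and to 25.0% against 25.5% at c = 20.

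**The case against.** The strongest reply is that the paragraph corrects itself. The sentence after the test opens by making it specific and names the close-other versus control contrast, and the Study Protocol gives the same contrast. A repeated-measures analysis can also hold target type as a within-person factor. On that reading the plan has one specification, and the problem arises only if an analyst ignores the next sentence. This largely stands: the intended outcome is recoverable. It does not cover the control trial type, which no passage identifies and without which the difference cannot be computed.

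A reader might infer from the first table that this trial's false-positive rate could reach 21–93%. The documents do not support that. Those rates need naproxen itself to change general reaction speed, which nothing in the documents says, and they rest on assumed SDs. Practice or fatigue common to both arms cancels in the time by condition test. Nor does the table show that the difference is the more powerful outcome.

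It can also be said that ANCOVA does not cure an unnamed outcome and departs from the form of the other planned tests. Both are true. It is a separate improvement that uses data already planned, and it is best adopted for all three primary outcomes together.

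**Conclusion.** The wording gap is real and should be fixed, but it is modest. The test sentence, taken literally, estimates a quantity other than the one hypothesised; the intended quantity can be inferred; the control trial type cannot. It would go too far to say that the plan has the wrong hypothesis or lacks one, or that the two readings would point in opposite directions. The direction is implied by the text, and the sign of the difference is only a labelling convention.

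The reason to prefer the difference is that it measures what the aim names. The general-speed percentages are illustrations only.

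The precision gain from baseline adjustment rests on randomisation and on r, which the documents do not give. It is large for low r, small by r = 0.9 and gone near 0.96. ANCOVA is therefore not better in every case, but the most it can lose here is about 1 percentage point of power.

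**What to change.** In the SAP's primary social-reward paragraph:

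- State that the dependent variable is each participant's mean reaction time to control minus mean reaction time to close other, at each session. Equivalently, specify the time by condition by target interaction.
- Name the trial type already used in the task as the control.
- Label undifferenced reaction time as descriptive.
- Compare the arms on the post-session difference adjusted for the baseline difference (ANCOVA), preferably in the same form for loneliness and for the ratings of negative social images.

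If the sponsor prefers to keep the planned test, the minimum is to keep time by condition on the defined difference score.

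The cost is SAP wording. No new data are needed, because the task is planned at both sessions. ANCOVA uses one degree of freedom (47 instead of 48). If adopted for this outcome alone, it also breaks uniformity with the other primary analyses.

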NCT Study Title: Inflammation and Daily Life Study

Grant Study Title: Can an anti-inflammatory medication reduce loneliness?

NCT: NCT03771612

Original Document Date: January 7, 2022

Modified with Requested Updates: December 20, 2024

Study Protocol

Due to the relationships between loneliness and a variety of poor health outcomes and mortality, loneliness is increasingly being recognized as an important public health issue. Despite the relevance of loneliness for health, including evidence suggesting the effects may be particularly pronounced for middle-aged adults, loneliness is a highly understudied topic in mid-life in need of further research. One potential mechanism for the effect of loneliness on health is inflammation. Lonely individuals have heightened inflammation, and inflammation can increase feelings of loneliness. Furthermore, loneliness and inflammation share similar psychological states, both marked by hypersensitivity to the social world, including increased sensitivity to both negative and positive social cues (i.e., social threat and social reward). Thus, by breaking the cycle between inflammation and loneliness, and altering the underlying hypersensitive psychological state, it is possible that an anti-inflammatory drug may lead to improvements in loneliness. However, to our knowledge, no studies have explicitly tested this. The objective of this study is to address this gap in the literature and test the effect of an anti-inflammatory medication on loneliness in a sample of middle-aged adults and to examine the social psychological mechanisms that may underlie any benefits.

This randomized double-blind placebo-controlled study will test the effect of an NSAID (naproxen) on loneliness and explore which psychological mechanisms are best targeted by an NSAID. Participants, all middle-aged adults screened for high levels of loneliness, will be randomized into a 2-week naproxen or placebo intervention. All participants will complete pre- and post-intervention sessions online to assess self-report psychological outcomes, inflammatory activity, and performance on behavioral tasks.

Participants will be men and women, ages 45-59, who all have high levels of loneliness. High loneliness scores will be assessed using the UCLA Loneliness Scale, with eligible subjects having a score of 41 or greater (approximately 20-25% of middle-aged adults), which has been previously used by our group to define a high loneliness group.

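### Does the unnamed control target in the social-reward primary let an effect on social reward cancel out of its own test?

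*Combined protocol and SAP*

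**What the plan says.** The Study Protocol's description of the baseline session has participants press a button when a target flashes, "in order to win money or see a close other or smiling stranger". Faster responses are taken as stronger anticipation of reward. The protocol adds that the team is "particularly interested in the difference in reaction times to close others vs. control targets".

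The Statistical Analysis Plan lists this outcome under Primary. The aim is general: "To examine whether naproxen reduces sensitivity to social reward". The model is a time by condition interaction, "interactions on reaction times to social reward (with faster reaction times indicative of greater reward"). A more specific expectation follows, that the naproxen arm will "show less of a difference in reaction times to viewing close others vs. control targets from pre- to post-intervention".

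The rationale at the start of the Study Protocol is also broad. It describes loneliness and inflammation as states of heightened social sensitivity, "including increased sensitivity to both negative and positive social cues (i.e., social threat and social reward").

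No section labels any target as the control. The IRB amendment of 5/2021 sets the size of the trial: "we will have a final sample of n=50".

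**The concern.** The three things a participant can win or see are money, a close other and a smiling stranger. Each is a reward, none is called a control, and no neutral trial is mentioned. If the stranger is the control, the primary contrast sets one social reward against another, while the stated aim is sensitivity to social reward as a whole. A drug that dulled the response to all friendly faces equally would leave the contrast unchanged, and a null result could be read as no effect on social reward. If money is the control, the contrast tests social against monetary reward, which is a different hypothesis. An unwritten choice could also, in principle, be made after the data are seen.

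**Working it through.** The plan gives no power, SD, effect size or significance level for this outcome, and the sample size is justified by cost. There is no figure to reproduce, so the check is algebra plus an illustration.

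**Algebra.** Let d be the naproxen-minus-placebo effect on the pre-to-post change in reaction time for a given target. The time by condition effect on the close-other versus control difference is

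effect tested = d_close − d_control.

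Take an assumed slowing of 20 ms for close others:

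| Control target | Assumed effect on control | Expected contrast |
|---|---|---|
| Smiling stranger, equally affected | 20 ms | 20 − 20 = 0 ms |
| Neutral or no-reward cue | 0 ms | 20 − 0 = 20 ms |
| Money, unaffected | 0 ms | 20 − 0 = 20 ms |
| Money, equally affected | 20 ms | 20 − 20 = 0 ms |

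The cancellation is real in the first row. The last row shows that money as control has the same weakness, against a different kind of shared effect.

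**Illustration of size.** From the documents: 50 participants randomised half and half, so 25 per arm. Assumed: two-sided 5% level, SD of the change in the contrast set to 1, d_close = 0.8 SD, and a share s of that effect also present in the control. The standard error is √(2/25) = 0.283, and by the normal approximation

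power ≈ Φ(0.8(1 − s)/0.283 − 1.96), plus a negligible lower tail except near s = 1.

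- s = 0: 0.8/0.283 = 2.83; Φ(0.87) = 0.81.
- s = 0.5: 0.4/0.283 = 1.41; Φ(−0.55) = 0.29.
- s = 1: expected contrast 0; both tails together give 0.05.

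At d_close = 0.5 SD the same three figures are 0.42, 0.14 and 0.05.

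**Choosing the control afterwards.** By simulation with no drug effect and equal noise on every target, reporting whichever of stranger or money is significant gives about 9.0% false positives instead of 5%. This shows what such a choice would cost. Nothing in the plan suggests that it would be made.

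**What the text supports.**

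1. The task is summarised in one sentence, as a revised form of a cited task. That sentence need not list every trial type, so a neutral or no-reward cue is not excluded.
2. The model sentence refers to reaction times to social reward without subtracting anything. On that reading nothing cancels. The sentence after it, and the protocol's stated interest, favour the difference.
3. The SAP speaks of viewing targets, and the protocol has participants win money but see faces. This makes money the least likely control and the stranger more plausible.
4. The SAP narrows its own aim: the specific expectation concerns close others. If the stranger is the control, the contrast isolates what is particular to a close relationship, which is a legitimate question.

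**The case for a change.** The strongest case for a change is that the control decides which hypothesis a primary outcome tests, and that naming it takes a sentence. The rationale and the aim speak of social reward generally, the stranger is the only other social target listed, and a fully shared effect would be invisible at any sample size. Reaction times for all three listed targets are collected anyway, so a non-social control could be made primary, with the stranger contrast as a secondary.

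Much of this stands. The control is unnamed in both places where it appears, and the algebra is right. If the stranger is the control, a null speaks only to reward specific to close others. The remedy is weaker than the diagnosis. The only non-social target listed is money, and with money as control an effect on reward in general cancels. The change would also replace the investigators' stated contrast with social versus monetary reward, which the plan does not put forward as its hypothesis.

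**Conclusion.** No change to the plan follows. The missing name is a gap in description that the investigators can fill, because they built the task and know its control condition. For the hypothesis they state specifically, about close others, the planned time by condition test on the difference is sound with any of the possible controls, provided the conclusion is confined to the contrast actually tested. Changing the primary control to a non-social target is a trade-off without clear gain.

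The possible loss is large only in one case: the stranger is the control, the difference is the outcome, and much of the drug effect is shared by both faces. Power at 25 per arm then goes from 0.81 to 0.29 with half shared and to 0.05 with all shared. With a neutral or no-reward cue that does not itself respond to the drug, or with no subtraction, the loss is nil. The algebra needs no assumptions. The power and false-positive figures rest on an assumed effect size, sharing fraction, noise pattern and significance level, none of which the documents give.

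### The test planned for loneliness at follow-up is a three-level time-by-condition interaction, which can be significant when the follow-up effect is zero

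*Combined protocol and SAP*

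**What the plan says.** The second secondary objective in the Statistical Analysis Plan reads "To examine whether naproxen reduces feelings of loneliness at follow-up (2 weeks post-intervention"). It therefore has a direction (a reduction) and a single time point. For this objective the plan will use repeated measures analyses to "examine time (pre- vs. post- vs. follow-up intervention) by condition (naproxen vs. placebo) interactions on loneliness".

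The primary loneliness objective has a parallel sentence with two times: "examine time (pre- vs. post-intervention) by condition (naproxen vs. placebo) interactions on loneliness".

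The Study Protocol describes the visit behind the follow-up objective: after the two-week intervention, "participants will be contacted again 2 weeks later to assess measures of loneliness". Nowhere do the documents name a pre-to-follow-up contrast, an arm comparison at follow-up, a simple-effects step, or a rule for reading the three-level interaction.

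**The concern.** With two times, the time-by-condition interaction has one degree of freedom and is itself the contrast of interest: the arm difference in change from pre to post. With a third time that equivalence is lost. The interaction then tests jointly whether the arm difference is the same at pre, post and follow-up, and it is false if the arms separate at post alone.

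Whether an effect outlasts the pills is the only question this analysis adds to the primary one, and an effect that fades once they stop is a plausible outcome. In that case the specified test may well be significant. Reported against an objective worded as a reduction at follow-up, it could be taken as evidence of lasting benefit. The plan does not prescribe that reading, but it contains nothing to prevent it.

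**Working it through.** **No figure to reproduce.** The plan attaches no power or effect size to this analysis. The sample of 50 was set by cost in the May 2021 IRB amendment.

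**Inputs from the documents.** Total n = 50. Allocation is equal ("half of the participants will take naproxen and half will take the same dose of placebo"), so 25 per arm. Three measurement times.

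**Assumptions, because the documents are silent.** Alpha 0.05 (two-sided for contrasts), complete data, SD 1 at each time, equal correlation ρ between times of 0.5 to 0.8, and a true effect e of 0.2 to 0.8 SD.

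**Power of the interaction.** Let δ be the naproxen-minus-placebo difference at pre, post and follow-up. The F test has 2 and 2(50 − 2) = 96 df, with noncentrality

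λ = (n/2) × Σ(δ_t − mean δ)² / (1 − ρ), n = 25 per arm.

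- Effect gone by follow-up, δ = (0, −e, 0): Σ = e²/9 + 4e²/9 + e²/9 = (2/3)e².
- Effect sustained, δ = (0, −e, −e): Σ = 4e²/9 + e²/9 + e²/9 = (2/3)e².
- Worsening on naproxen at follow-up only, δ = (0, 0, +e): Σ = (2/3)e².

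The three patterns give the same λ, hence the same power. For e = 0.5 and ρ = 0.5, λ = 12.5 × 0.1667 / 0.5 = 4.17 and power is 42%. At ρ = 0.8, λ = 12.5 × 0.1667 / 0.2 = 10.42 and power is 82%.

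**Chance of a significant interaction when the follow-up effect is zero** (ranges over ρ = 0.5 to 0.8):

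| Post-only effect | 25 per arm | 20 per arm | 25 per arm, multivariate test (2 and 47 df) |
|---|---|---|---|
| 0.2 SD | 10–19% | 9–16% | 10–18% |
| 0.3 SD | 17–38% | 15–31% | 17–37% |
| 0.5 SD | 42–82% | 34–72% | 41–81% |
| 0.8 SD | 83–99.7% | 73–99% | 82–99.6% |

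Simulation of 40,000 trials per scenario at 25 per arm agrees with the formula within 0.5 points. In those trials, ANCOVA at follow-up rejects in 4.8–5.2% and the change-score t-test in 4.8–5.1%. With no effect at any time, all three tests reject in 4.8–5.0%.

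**Power for an effect of 0.5 SD sustained to follow-up, 25 per arm.** The change-score contrast has noncentrality 0.5 / [√(2(1 − ρ)) × √(2/25)] on 48 df; at ρ = 0.5 this is 0.5 / (1 × 0.283) = 1.77. ANCOVA replaces √(2(1 − ρ)) with √(1 − ρ²) and has 47 df; at ρ = 0.5 this is 0.5 / (0.866 × 0.283) = 2.04, before a small loss for chance baseline imbalance, which the table includes.

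| ρ | Interaction | Baseline-adjusted contrast | Change-score contrast |
|---|---|---|---|
| 0.5 | 42% | 51% | 41% |
| 0.6 | 51% | 57% | 49% |
| 0.7 | 64% | 67% | 61% |
| 0.8 | 82% | 81% | 78% |

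Any gain in power comes from adjusting for baseline, not from moving to a single contrast.

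**The case against.** **The omnibus test is inferred.** The plan says only repeated measures and interactions. A mixed model with categorical time and pre as reference would fit the sentence, and one of its coefficients is the follow-up contrast. This stands in part: the wording does not exclude it. But the plan does not say which component answers the objective, and the omnibus test is the most natural reading. The plural does not point to separate contrasts, since the primary sentence uses it where only one contrast exists.

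**The significant results in the first table are not false positives for the interaction.** This is correct. With a real post effect the interaction null is false and rejection is right. The error arises only if the result is taken as an answer about follow-up, and a reader who looks at the means at all three times would probably avoid it.

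**The percentages rest on assumed inputs, and exact equality of power needs equal correlations.** Also correct. With correlation decaying over time (first-order autoregressive) and a 0.5 SD effect, the multivariate interaction has 48% power for a post-only effect against 33% for a sustained one at ρ = 0.5, and 91% against 68% at ρ = 0.8. Equality fails, but the test then favours the effect that has vanished, which does not help the plan.

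**Naming the contrast would suffice; covariate adjustment is a separate preference.** True for validity. Baseline adjustment is what avoids a small loss of power, and sex defines the randomization strata ("males and females will be randomized separately in permuted blocks of 4").

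**Conclusion.** The concern holds. The analysis specified for follow-up loneliness does not isolate the effect at follow-up, and no other analysis in the documents does. That conclusion needs none of the numerical assumptions: any non-zero effect at post alone makes the interaction null false. The size does depend on them. At 25 per arm, alpha 0.05, complete data and equal correlations of 0.5 to 0.8, a significant interaction with zero follow-up effect occurs in 10–19% of trials for a post effect of 0.2 SD, rising to 83–99.7% for 0.8 SD.

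The consequence is confined to one secondary objective and is a risk of misreading, not a prescribed error. It should be corrected before the follow-up result is interpreted.

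**What to change.** Replace the analysis sentence for this objective with one that:

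- names the 1-df naproxen-minus-placebo difference in loneliness at follow-up as the test;
- estimates it by ANCOVA on baseline loneliness, or as the follow-up contrast from a mixed model with baseline as a covariate or constrained equal across arms, with the sex stratum included;
- states alpha, and reports the estimate, its direction and a 95% CI;
- keeps the three-level interaction as a description of the time course only.

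The Study Protocol also says that loneliness analyses will control for depressive symptoms. The new sentence should say whether that applies to this contrast; the power figures above do not include it.

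The cost is one sentence in the plan, with no new data. For a sustained 0.5 SD effect, the baseline-adjusted contrast has 51–67% power against 42–64% for the interaction at ρ = 0.5 to 0.7, and 81% against 82% at ρ = 0.8. Without baseline adjustment the contrast is slightly weaker than the interaction, at 41–78% against 42–82% over ρ = 0.5 to 0.8.
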